Specific aims: Does the use of perioperative pharmacologic agents (subcutaneous heparin; 5,000 units given before surgery and every 8 hours after surgery until discharge), compared to IPCs alone, for RP for prostate cancer:

1. Prevent the occurrence of symptomatic VTE following surgery? (primary efficacy outcome)
2. Increase the incidence of clinically significant lymphocele? (primary safety outcome)
3. Increase the incidence of clinically significant hematoma? (primary safety outcome)
4. Increase the incidence of major bleeding following surgery? (primary safety outcome)
5. Prevent the occurrence of any VTE (asymptomatic or symptomatic) following surgery? (secondary outcome)
6. Increase estimated blood loss during surgery? (secondary outcome)
7. Increase surgical drain output after surgery? (secondary outcome)

8. Lead to potential surveillance bias measured by increased or decreased use of diagnostic imaging for VTE relative to symptoms (e.g. lower extremity Duplex ultrasound, spiral CT angiography, V/Q scan, etc.)? (secondary outcome)

3. Background (briefly describe pre-clinical and clinical data, current experience with procedures, drug or device, and any other relevant information to justify the research)

An estimated 180,000 new cases of prostate cancer were diagnosed in 2016, and about 90,000 radical prostatectomies are performed in the United States annually [1-3]. Since the year 2000, a sharp change in practice patterns has shifted the traditionally open radical prostatectomy (RP) procedure to current practice where the great majority (likely >70%) are robotic-assisted laparoscopic RPs (RALRP) [3]. According to most guidelines, undergoing RP by any approach classifies a patient as high-risk for venous thromboembolism (VTE), including deep venous thrombosis (DVT) and pulmonary embolism (PE), and would lead to implementation of appropriate intermittent mechanical pneumatic compression devices (IPCs) and pharmacologic prophylaxis [4-8].

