The secondary outcomes (all regarded separately) will be estimated blood loss from surgery, total surgical drain output after surgery (for patients with surgical drains), the overall incidence of VTE (asymptomatic or symptomatic) determined from the subcohort undergoing lower extremity Duplex screening ultrasound, and surveillance bias (measured by use of postoperative diagnostic imaging). Estimated blood loss will be recorded from the anesthesia data report from surgery. Total surgical drain output will be recorded based on ins and outs flowsheets routinely recorded by nurses when emptying drains. Surveillance bias will be determined by recording the type and frequency of postoperative imaging performed while a patient is in the hospital or within 30 days of surgery after discharge.

The overall rate of VTE will only be determined for patients in the subcohort. The asymptomatic VTE will be determined based on the results of the screening lower extremity Duplex ultrasound for asymptomatic DVTs. The overall rate of VTE will be determined by adding the number of asymptomatic VTE events to the number of symptomatic VTE events experienced in the subcohort.

d. Statistical plan including sample size justification and interim data analyses.

Pharmacologic VTE prophylaxis can be expected to prevent between 67% to 75% of DVTs [33]. Given the lowest expected primary outcome event rate will be for VTE, the trial sample size will be based on a power of 80% ($\beta=0.2$) and one-sided α of 0.05 for prevention of post-operative VTE with pharmacologic prophylaxis reducing the rate from 5% to 1.5%. Including two interim analyses of the primary endpoint as outlined in the Interim Analyses section below, the total sample size needed will be 666 (333 per treatment arm) based on 2000 simulations for 82% power (exact α -spending and futility boundaries are outlined below). As mentioned above, the primary efficacy analysis will compare symptomatic VTE rates at the 30-day follow-up for all patients. Secondary analyses will be conducted to compare secondary outcomes between treatment arms at the completion of the study as well. It is expected that during full-time patient enrollment, the study would require about 2 years to accrue patients assuming 50% enrollment.

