Two planned interim analyses of the primary endpoint will be conducted, after one-third and two-thirds of patients have undergone RP. Early stopping for efficacy or futility will be assessed at these time points. Details are provided below under Interim Analyses.

Statistical analyses: The treatment and control groups will be compared to identify any imbalance after randomization in relevant characteristics. Comparisons will include factors such as age, race, BMI, comorbidities, prostate volume, tumor stage, operative time, and blood loss. Discrete factors will be compared with chi-squared test, and continuous factors will be compared with t-test or Wilcoxon ranksum test if data do not conform to a Gaussian distribution. Analysis of the primary outcome (symptomatic VTE) will compare 30 day post-RP rates between the treatment and control groups, using chi-squared test. Logistic regression will be used if adjustment is required for any potential confounders not balanced by randomization, with the treatment effect estimated by the odds ratio and 95% confidence interval. Similar comparison of univariate rates, and adjusted odds ratios will be used for the 3 primary safety endpoints (lymphocele, hematoma, occurrence of major bleeding), and for the secondary outcome of any VTE (restricted to patients who undergo the 30 day lower extremity Duplex ultrasound). Secondary endpoints with a continuous metric (blood loss, surgical drain output, number of imaging tests (surveillance bias)) will be compared in univariate fashion using t-test or Wilcoxon ranksum, and adjusted analyses will use linear regression. Note that analysis of drain output is confined to patients with drains placed, so it is not protected by the randomization, potentially limiting interpretability if the number of patients is small and confounding factors are not well balanced. All analyses of primary and secondary outcomes will be based on intention to treat (ITT). Per protocol analyses will also be conducted, but treatment success will be based on ITT.

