Additional subanalyses (both ITT and per protocol) will be performed with stratification by arm compliance (proportion of scheduled subcutaneous heparin doses administered), performance of pelvic lymphadenectomy (including number of nodes removed), performance of open or robotic surgery (including differences in operative time), and other demographic and comorbidity criteria (including history of VTE, cancer, and other risk factors included in the Caprini Score) to identify patients at highest risk for VTE. Surveillance bias will also be evaluated, as mentioned above, by the differential performance of diagnostic imaging.

e. Interim Analyses.

Two interim analyses of the primary endpoint are planned with potential early stopping for efficacy or futility. O'Brien-Fleming boundaries were used, as implemented in PASS v. 11 (NCSS Software, Inc., Kaysville, UT). The total sample size needed for 82% power with a 1-sided test is 666 (333 per treatment arm), based on 2000 simulations. The interim analyses will be conducted after 1/3 and 2/3 of patients are enrolled (222 and 444, respectively). Alpha-spending at the 2 interim analyses and final analysis is .001,

.015, and .033 (cumulative alpha spent .001, .015, .048), respectively. The futility boundaries at the 1st and 2nd interim analyses, and final analysis are $p=0.816$, 0.272 , and 0.070 , respectively.

At each interim analysis the rates of the 3 safety endpoints (lymphocele, major bleeding, and hematoma) will also be evaluated and 95% confidence intervals calculated. Unacceptable rates for these endpoints are $\geq 15\%$, $\geq 5\%$, and $\geq 10\%$, respectively. If lower 95% confidence bounds meet or exceed these unacceptable rates the trial will be halted for further review and consideration of early stopping.

8. Risks

- a. Medical risks, listing all procedures, their major and minor risks and expected frequency.

Administration of subcutaneous heparin:

1. Major risks:

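### The interim safety rule in Section 7e does not compare the arms or say whether rates are per arm or pooled, so it can miss a several-fold heparin excess when baseline rates are low

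*Combined protocol and SAP*

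**What the plan says.** Section 2 (Objectives) frames the safety questions as comparisons of heparin with pneumatic compression alone. For bleeding the aim reads "Increase the incidence of major bleeding following surgery? (primary safety outcome"; lymphocele and hematoma are worded in the same way.

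Section 7d plans a between-arm analysis of these outcomes: "Similar comparison of univariate rates, and adjusted odds ratios will be used for the 3 primary safety endpoints". No interim action depends on it.

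Section 7e governs the two interim looks, at 222 and 444 patients. On safety it says "At each interim analysis the rates of the 3 safety endpoints (lymphocele, major bleeding, and hematoma) will also be evaluated and 95% confidence intervals calculated". It then calls rates of at least 15% (lymphocele), 5% (major bleeding) and 10% (hematoma) unacceptable, and gives the trigger: "If lower 95% confidence bounds meet or exceed these unacceptable rates the trial will be halted for further review and consideration of early stopping". It names no arm, difference or ratio, and does not say whether the arms are pooled.

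Section 7b puts symptomatic lymphocele at about 10% at most. No baseline is given for hematoma or major bleeding.

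**The concern.** The trial has a concurrent randomised control, but its only numerical interim safety trigger does not use it. The trigger asks whether a rate has been shown to exceed a fixed ceiling, whereas the aims ask whether heparin raises the rate. The two questions can have different answers. If an outcome is uncommon without heparin, a large relative increase may leave the heparin rate at or below the ceiling, or above it without the lower bound clearing it. Pooling the arms would dilute a heparin effect further. At stake is whether a heparin-related excess is formally flagged at a look that is already planned, or only at the final analysis.

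**Working it through.** **Inputs.** Looks at 222 and 444 patients and 1:1 allocation (7e) give 111 and 222 per arm, taken here as having complete 30-day outcomes. Limits are 15%, 5% and 10% (7e). Baselines are assumed, except lymphocele up to 10% (7b).

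**The plan's own figure.** The safety rule has no stated operating characteristics. The sample size does: "The total sample size needed for 82% power with a 1-sided test is 666 (333 per treatment arm), based on 2000 simulations". For 5% v 1.5%, n = 333 per arm and one-sided 0.05, ignoring the looks, the standard error is 0.01374 under the null and 0.01368 under the alternative. Power = Φ[(0.035 − 1.645 × 0.01374)/0.01368] = Φ(0.91), about 82%. This agrees. It concerns efficacy and matters here only because it fixes the interim sizes.

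**Counts needed to halt.** The exact (Clopper-Pearson) lower 95% limit for x events in n is the 0.025 quantile of Beta(x, n − x + 1). The smallest x whose limit reaches the ceiling is:

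| Outcome (limit) | One arm, n = 111 | One arm, n = 222 | Pooled, n = 222 | Pooled, n = 444 |
|---|---|---|---|---|
| Bleeding (5%) | 11 (9.9%) | 19 (8.6%) | 19 | 33 |
| Hematoma (10%) | 19 (17.1%) | 32 (14.4%) | 32 | 58 |
| Lymphocele (15%) | 25 (22.5%) | 45 (20.3%) | 45 | 83 |

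Wilson, Wald or one-sided 95% bounds move these counts by only 1 to 3 events.

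**Chance of a halt by look 2.** With halting counts a and b at the two looks, P(halt) = 1 − Σ over x < a of P(X₁ = x) × P(X₂ ≤ b − 1 − x), where X₁ and X₂ are the events before and after look 1. For one arm both are Binomial(111, p).

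With the true heparin rate exactly at the limit, P(halt) is 3.3% (bleeding), 3.1% (hematoma) and 3.6% (lymphocele). This needs no baseline assumption. A 50% chance of a halt needs a true heparin rate of about 8.2%, 14.1% or 19.8% respectively.

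**Comparison with a difference check.** The last column is the simulated chance (at least 200,000 trials per row) that the lower Newcombe 95% limit for heparin minus control exceeds 0 at either look.

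| Control v heparin | Present rule, heparin arm | Present rule, pooled | Difference check |
|---|---|---|---|
| Bleeding 1% v 5% | 3% | <0.1% | 73% |
| Bleeding 2% v 6% | 11% | 0.2% | 61% |
| Bleeding 3% v 9% | 67% | 15% | 79% |
| Bleeding 5% v 10% | 82% | 58% | 55% |
| Hematoma 3% v 10% | 3% | <0.1% | 88% |
| Hematoma 5% v 15% | 64% | 3% | 96% |
| Lymphocele 5% v 15% | 4% | <0.1% | 96% |
| Lymphocele 10% v 20% | 53% | 3% | 86% |
| Lymphocele 10% v 30% | ~100% | 80% | ~100% |

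**One concrete split.** Take 10/111 bleeds on heparin and 0/111 on control at look 1. The exact lower bound for heparin is 4.4%, below 5%, so there is no halt. Pooled, 10/222 is well short of 19. Fisher's exact p is 0.0016. The Newcombe lower limit is 0.0901 − √[(0.0901 − 0.0497)² + 0.0335²] = 0.038, above 0.

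**False flags from the difference check.** With equal arms, the chance of a flag over both looks is about 1.1% at a 1% rate, 2.5% at 2%, 3.1% at 3%, 3.6% at 5% and 3.9% at 10%. For bleeding 2%, hematoma 5% and lymphocele 10%, taken as independent, the chance of any flag is 1 − 0.975 × 0.964 × 0.961 = 9.7%.

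**The case against.** Absolute ceilings are a legitimate form of monitoring, and at higher baselines this one works. A reader might infer that a several-fold excess would usually go unnoticed. The documents do not support that. At the plan's own upper lymphocele figure, a threefold excess (10% v 30%) halts almost every trial per arm. Bleeding 3% v 9% halts 67% and hematoma 5% v 15% halts 64%. For bleeding 5% v 10% the present rule acts more often than the difference check (82% v 55%). The scenarios with about a 3% halt all put the heparin rate on the ceiling, where a lower-bound rule fires rarely by construction. Section 7d also says VTE, at 5% in control, has the lowest expected primary outcome rate. If that covers the safety outcomes, the low baselines used above run against the plan. All of this stands, and it limits the point to low baselines or pooled rates. The 7d remark is not a full answer, however: it would put expected bleeding at or above the 5% that 7e calls unacceptable.

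A reader might also infer that the plan never compares safety between arms. It does so in 7d; only the interim trigger lacks a comparison. Section 8c adds reporting of unanticipated problems to the IRB, and postoperative heparin is unblinded, but neither supplies a comparative check.

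A third inference is that the rule would wrongly halt for a high background rate. Lymphocele at 22% in both arms would halt 78% of trials on the heparin-arm reading. But 22% is over twice the plan's figure, and pausing at a rate the plan calls unacceptable is defensible whatever the cause.

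Finally, a hard halt whenever a lower limit exceeds 0 would be too sensitive. It would fire at 5/111 v 0/111 (Fisher p = 0.06) and could halt nearly 10% of trials with no heparin effect. That objection is accepted in the fix.

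**Conclusion.** The point holds in a limited form. The interim trigger is non-comparative and leaves per-arm or pooled unstated. On the heparin-arm reading, a true heparin rate equal to a limit halts only 3.1% to 3.6% of trials by look 2; that result depends only on the interim sizes and the type of bound. Whether a several-fold excess is missed depends on the baseline. At roughly threefold to fivefold it is usually missed for bleeding at 1% to 2%, hematoma at 3% and lymphocele at 5% (halts in 3% to 11% of trials in the cases tabulated), and usually caught at higher baselines if the arms are read separately. Pooling widens the gap: lymphocele 10% v 20% falls from 53% to 3%. The hematoma and bleeding baselines are assumptions. This is a worthwhile improvement to patient protection, using data already in hand at each look; it does not show the existing limits to be wrong.

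**What to change.** In Section 7e, state that the three existing limits, unchanged, are applied to each arm separately and not to pooled rates. Add that at each look the heparin-minus-control risk difference with a 95% confidence interval (for example Newcombe) is computed for lymphocele, hematoma and major bleeding, and that a lower limit above 0 sends the data for safety review without automatically halting the trial. Stating the expected baseline rates for hematoma and bleeding beside the limits would let the rule's behaviour be judged.

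The cost is a few sentences and one extra table per look. The downside is about 1% to 4% false flags per outcome over both looks, up to about 9% to 10% for all three if independent, each leading to a review only. The change does not address halts caused by a high background rate in both arms, because the absolute limits stay as they are.
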